9. STATISTICAL METHODS AND CONSIDERATIONS

9.1. Analysis Plan

An intention to treat analysis will be performed. Prevalence of any adverse event, treatment-related adverse events, and serious and/or fatal adverse events will be calculated. Secondary analyses assessing pairwise differences in pre- and post-interventional changes in symptom scores will also be performed to identify trends and as the basis for future power analyses. Categorical variable data will be summarized as frequencies with Agresti-Coull intervals as applicable. Quantitative variable data will be summarized as medians with interquartile ranges. Spearman's rank correlation coefficient, two-sided Student's t-test, chi-square tests, and nonparametric equivalences may be conducted at 0.05 significance level.

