5.3. Number of Subjects to be Evaluated

Up to 10 patients will be evaluated. Sample size was determined off of norms for phase 1 trials, as there lacks sufficient data to conduct a power analysis. Patients who are lost to follow-up and/or withdraw early from the study will not be replaced.

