6.4. Screening

Upon enrollment, the neurological provider will be asked to verify past medical history (i.e., tobacco use, obesity status, past traumatic brain injury, diabetes mellitus, hypertension, hyperlipidemia) and current medications during the clinical encounter. Patients would undergo a pre-treatment serum metabolic blood panel to document baseline serum glucose levels, which is a routine biomarker to assess prior to administering glucocorticoid medications. Specific for research purposes only, patients would also be asked to score baseline MIDAS, 4-point verbal rating scale, and 11-point numeric pain scores (Appendix G). Patients will be instructed to keep a Study Diary, and will be instructed to record migraine episodes and any adverse events with date of onset, duration, and description for four weeks before and three months after treatment.

Patients with baseline serum glucose of above 400 mg/dL will fail screening procedures and not be included within the study due to elevated risk of acute exacerbation of steroid hyperglycemia during methylprednisolone administration.

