7. STUDY TREATMENT, PROCEDURES, AND GUIDELINES

7.1. Study Intervention

After baseline screening assessment, patients will be scheduled within one month for investigational drug administration. Xylocaine®-MPF will be prepared for administration of 40 mg of active lidocaine hydrochloride per dose as described in Section 3.1.4. A total of two doses (40 mg lidocaine hydrochloride per dose; 80 mg total) of lidocaine hydrochloride will be prepared for the injection of each dose into each middle meningeal artery (left and right). SOLU-MEDROL® will be prepared for administration of 20 mg of active methylprednisolone sodium succinate as described in Section 3.1.4. A total of two doses (20 mg methylprednisolone sodium succinate per dose; 40 mg total) of methylprednisolone sodium succinate will be prepared for the injection of each dose into each middle meningeal artery (left and right). No placebo agents will be used during the study. Agents will not be blinded. Agents will be prepared and stored per instructions contained within Section 16 (HOW SUPPLIED/STORAGE AND HANDLING) of the Prescribing Information and manufactures' guidelines contained within the packaging insert.

The treatment will be administered in the Acute Stroke and NeuroInterventional Suite at Cooper University Health Care. The care team will include an experienced neurointerventional physician with extensive experience in proper catheter placement and technical specifications necessary for the procedure below, certified and licensed angiography technicians, a dedicated anesthesiology care team, pharmacy team, and nursing team comprised of neurocritical care certified nurses (including post-procedural recovery and observation). Within the immediate treatment area, availability to resuscitative equipment and continuous vital sign monitoring, including rapid cycling continuous blood pressure monitoring (with measurements at least every 5 minutes), continuous pulse oximetry, respiratory rate, continuous heart rate monitor, and electrocardiographic monitoring, will be ensured. For safety, patients may be sedated using institutional monitored anesthesia care (MAC) protocol under the care of a licensed anesthesiologist, and thus will not require intubation. Patients will be monitored continuously throughout the procedure and for four hours post-operatively in a dedicated post-angiography care unit.

The following steps will be performed interprocedurally:

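### The primary adverse event rates are set on an intention-to-treat basis in a single-arm trial, so patients who leave between enrolment and dosing would lower them

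*Combined protocol and SAP*

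**What the plan says.** Section 9.1 names a single analysis basis and goes straight on to the primary safety measures: "An intention to treat analysis will be performed. Prevalence of any adverse event, treatment-related adverse events, and serious and/or fatal adverse events will be calculated". Proportions are to be given with intervals: "Categorical variable data will be summarized as frequencies with Agresti-Coull intervals as applicable". The intention-to-treat population is not defined, and no safety, dosed or as-treated set appears anywhere.

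The steps before dosing are described in three places:

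- Section 6.4 ties the baseline work to enrolment: "Upon enrollment, the neurological provider will be asked to verify past medical history". The blood panel, baseline scores and start of the diary follow.
- Section 7.1 places dosing later: "After baseline screening assessment, patients will be scheduled within one month for investigational drug administration". Table 1 and Section 7.2.2 put it about 4 weeks after Visit 1.
- Section 5.4 gives about 4 months from enrolment to the end of follow-up.

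On numbers, Section 5.3 says "Up to 10 patients will be evaluated" and "Patients who are lost to follow-up and/or withdraw early from the study will not be replaced". On event collection, Section 8.1 defines an adverse event for a patient who has been given a product and opens the SAE period once the study drug has been administered. The diary (Sections 6.4 and 7.2.1) also asks for adverse events in the four weeks before treatment.

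**The concern.** Intention to treat preserves a randomised comparison. This trial has one arm and no randomisation (Section 2), so there is no comparison to preserve. For a drug safety rate, its main consequence is to admit patients who were never exposed.

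Safety is the primary outcome (Section 4.1), and Section 3.1 presents the results as the basis for larger studies. Undosed patients in the denominator would make the SAE and drug-related rates look lower, and their upper limits tighter, than the exposure supports. The error runs in the reassuring direction. With at most 10 patients, each undosed patient is a tenth of the denominator.

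**Working it through.** **Is there a gap in which patients can be lost?** Section 5.4 gives about 4 months from enrolment to the end of follow-up, and the last visit is about 3 months after dosing. The difference, 4 − 3 = about 1 month, agrees with the interval in Sections 7.1 and 7.2.2. Enrolment therefore precedes dosing by about 4 weeks.

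**Can an undosed patient contribute an event?**

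- SAE: no. The collection period in Section 8.1 has not opened.
- Drug-related event: no. There is no drug to which it could be attributed.
- Any adverse event: unclear. The definition in Section 8.1 points to treated patients, but the diary records pre-dose events and the plan does not say whether they count.

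**Inputs.** N = 10 (Sections 2 and 5.3). It comes from phase 1 norms without a calculation, so there is no figure of the plan to reproduce. The interval method is Agresti-Coull (Section 9.1); its level is not stated, and 95% is assumed. The number enrolled but never dosed, u, is not given; 0 to 3 is assumed.

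**Formulas.** With x events, all in dosed patients, the reported rate is x/N and the dosed rate is x/(N − u). So

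reported rate = dosed rate × (N − u)/N.

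For Agresti-Coull with z = 1.96 (z² = 3.84): ñ = n + z², p̃ = (x + z²/2)/ñ, limits p̃ ± z√(p̃(1 − p̃)/ñ).

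Example, 0 of 10: ñ = 13.84, p̃ = 1.92/13.84 = 0.139, half-width 0.182, upper limit 32.1%. Example, 0 of 8: ñ = 11.84, p̃ = 1.92/11.84 = 0.162, half-width 0.210, upper limit 37.2%.

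**Results.** The reported figures on 10 patients are 20.0% (4.6–52.1%) for 2 events and an upper limit of 32.1% for zero events, whatever u is.

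| Undosed u | Dosed n | (10 − u)/10 | Relative understatement | 2 events, rate in dosed (95% interval) | 0 events, upper limit in dosed |
|---|---|---|---|---|---|
| 0 | 10 | 1.0 | 0% | 20.0% (4.6–52.1%) | 32.1% |
| 1 | 9 | 0.9 | 10% | 22.2% (5.3–55.7%) | 34.5% |
| 2 | 8 | 0.8 | 20% | 25.0% (6.3–59.9%) | 37.2% |
| 3 | 7 | 0.7 | 30% | 28.6% (7.6–64.8%) | 40.4% |

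**Sensitivity to N.** Section 9.2 calls 10 patients 50%, which implies 20 and conflicts with Sections 2 and 5.3. That is a separate matter. If N were 20, each undosed patient would lower the rate by 1/20 = 5% instead of 10%.

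**The case against.** The plan never says that undosed patients are counted, still less that they are counted as event-free. The intention-to-treat population is undefined. The adverse event definition and the SAE window both presuppose a treated patient. Section 2 gives the 10 subjects in its treatment-group row and puts subject involvement at 90 days, which would fit counting from dosing. A denominator of dosed patients is therefore a possible reading. This stands as a limit on the claim: the dilution follows from the usual meaning of the term, not from an explicit rule. It does not remove the problem, because the primary denominator is then left open and the only term used for it points to the less suitable set.

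A reader might also infer three stronger points that the documents do not support:

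- *That screen failures enter the denominator.* Section 6.4 says that patients above the glucose limit are not included in the study, Section 2 makes enrolment depend on eligibility, and Visit 1 assigns only a screening number. Only patients who pass screening and leave before dosing are at issue.
- *That a failed catheterisation is mere dilution.* Such a patient has faced the access and sedation risks in Section 3.4 and is informative about the procedure, though not about the drugs.
- *That non-replacement is part of the error.* It is a stated design choice, and Section 5.3 sets 10 as a maximum. It does cost information: the chance of seeing at least one event with a true rate of 10% is 65.1% with 10 dosed and 57.0% with 8. Changing it is not needed to remove the bias.

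Finally, the analysis is descriptive, no decision threshold is tied to the rate, and the intervals are wide and overlap heavily on either denominator. That limits the severity.

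**Conclusion.** The concern holds for SAEs and drug-related events, given the usual meaning of intention to treat. Those rates would be understated by u/10 in relative terms: 10%, 20% or 30% for 1, 2 or 3 undosed patients. With zero events the upper limit would be too low by 2.4, 5.1 or 8.3 percentage points (34.5, 37.2 or 40.4 minus 32.1). For any adverse event the direction cannot be settled until the plan says how pre-dose diary events are handled. The size is conditional on an unknown number of undosed patients and is zero if all 10 are dosed.

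It would go too far to say that the plan explicitly counts untreated patients as event-free; the text leaves that to convention. This is a should-fix point: the primary denominator ought to be based on exposure and fixed in advance.

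**What to change.** In Section 9.1:

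- Use all patients who received any study drug as the denominator for the primary adverse event prevalences, in place of intention to treat.
- Report the number enrolled but not dosed.
- Report procedure-related events separately, among all patients in whom the procedure was started.
- State that pre-dose diary events are listed separately and not counted in the primary prevalences.

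In Section 8.1, align the SAE collection period with the procedure-started set, so that events before the drug is given are captured. Without this, a patient with a serious access complication and no drug would be in that denominator while the event fell outside the collection period.

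A count of patients dosed on one side and on both sides would be a useful reporting addition, but the correction does not depend on it.

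The cost is a few sentences of protocol text. If some patients are not dosed, the stated rates become slightly less favourable and the intervals wider. No change to the number of patients is needed.

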9.2. Interim Analysis

One interim analysis is planned for formal evaluation of safety during phase 1. Interim analysis will be performed when a total of 10 patients (50%) have completed Study Visit 3 (1 week follow-up after study treatment).

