2. PROTOCOL SUMMARY

Name of Drug(s)	Lidocaine hydrochloride (Xylocaine®-MPF); methylprednisolone sodium succinate (SOLU-MEDROL®)	
Treatment Group/Sample Size	10 total subjects	
Design	Open-label, non-randomized study	
Estimated Length of Subject Involvement	90 days	
Route of Administration	Intra-arterial	
Regimen	40 mg lidocaine/20mg methylprednisolone co-administered into each middle meningeal artery (left and right side) once	
Primary Objective	This study will evaluate the safety of a co-administration of intra-arterial lidocaine and methylprednisolone for patients with intractable migraine. In addition, an examination of pain-related symptomatic relief per pain score scales will be assessed.	
Study Population	10 adults over the age of 18 with a diagnosis of intractable migraine without aura, defined as failure of four treatment trials, will be enrolled in the study if they meet inclusion and exclusion criteria and are willing to participate in the study.	
Multicenter	No	
Blinding	None/Open-label	
Randomization	None/Non-randomized	
Primary Safety Variable	Adverse Events	
Primary Efficacy Variable	y Variable Difference in pre- and post-drug MIDAS, 4-point verbal pain scale, and 11-point numeric pain scale scores.	

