8. DATA SAFETY MONITORING

8.1. Safety Monitoring Plan

Data safety monitoring will be undertaken jointly by the Institutional Review Board and Investigator, including training all co-investigators to report research-related adverse events to Investigator within 12 hours. A safety report to the Institutional Review Board after either

reaching half of anticipated enrollment (10 subjects) or eight months following trial start, whichever event occurs first, will be prepared.

An adverse event (AE) is any untoward medical occurrence in a clinical investigation of a patient administered a pharmaceutical product and that does not necessarily have a causal relationship with the treatment. An AE is therefore any unfavorable and unintended sign (including an abnormal laboratory finding), symptom or disease temporally associated with the administration of an investigational product, whether or not related to that investigational product. An unexpected AE is one of a type not identified in nature, severity, or frequency in the current Prescribing Information or of greater severity or frequency than expected based on the information in the Prescribing Information.

The Investigator will probe, via discussion with the subject, for the occurrence of AEs during each subject visit and record the information in the site's source documents. Adverse events will be recorded in the patient study records. Adverse events will be described by duration (start and stop dates and times), severity, outcome, treatment and relation to study drug, or if unrelated, the cause.

AE Severity

The National Cancer Institute's Common Terminology Criteria for Adverse Events (CTCAE) Version 3.0 will be used to assess and grade AE severity, including laboratory abnormalities judged to be clinically significant. The modified criteria can be found in the study manual. If the experience is not covered in the modified criteria, the guidelines shown in Table 2 below should be used to grade severity.

Severity (Toxicity Grade)	Description
Mild (1)	Transient or mild discomfort; no limitation in activity; no
	medical intervention or therapy required. The subject may be
	aware of the sign or symptom but tolerates it reasonably well.
Moderate (2)	Mild to moderate limitation in activity, no or minimal medical
	intervention/therapy required.
Severe (3)	Marked limitation in activity, medical intervention/therapy
	required, hospitalizations possible.

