Consistent with federal regulations and in accordance with standard operating procedures and policies of the Cooper University Health Care Institutional Review Board (IRB), all potential unanticipated problems that are 1) unforeseen and 2) indicate that participants are at increased risk of harm will be promptly reported to the Cooper University Health Care IRB. The Investigator will report internal and external AEs to the Cooper University Health Care IRB within 7 days of discovery that meet above criteria for an unanticipated problem requiring prompt reporting to the IRB. SAEs meeting prompt reporting criteria will be reported to the Cooper University Health Care IRB within 7 days of notification. Full reports will include: a) whether the occurrence of the adverse event alters the risk-benefit relationship of study participation, b) whether the protocol and/or consent form require modification, and c) whether any additional information needs to be given to the subjects who are already enrolled. Per federal regulations, SAEs meeting prompt reporting criteria will be reported within 7 calendar days if life-threatening or fatal or within 15 calendar days for all other types of qualifying reportable events to the appropriate regulatory body (i.e., FDA).

Monitoring visits will be conducted by representatives of the Sponsor according to the U.S. CFR Title 21 Parts 50, 56, and 312 and ICH Guidelines for GCP (E6). The Investigator grants permission to appropriate regulatory authorities to conduct on-site monitoring and/or auditing of all appropriate study documentation.

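### The one formal interim safety analysis is set at 10 patients, labelled 50%, in a trial of at most 10, so it falls after the last planned dose or never happens

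*Combined protocol and SAP*

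**What the plan says.** The Protocol Summary (Section 2) gives the sample size as "10 total subjects". Section 5.3 agrees: "Up to 10 patients will be evaluated". It adds: "Patients who are lost to follow-up and/or withdraw early from the study will not be replaced".

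Section 9.2 then states: "One interim analysis is planned for formal evaluation of safety during phase 1". The trigger is: "Interim analysis will be performed when a total of 10 patients (50%) have completed Study Visit 3". Visit 3 is the week-1 follow-up, and each patient is treated in a single session at Visit 2.

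Section 8.1 separately requires a safety report to the IRB, on "reaching half of anticipated enrollment (10 subjects) or eight months following trial start, whichever event occurs first, will be prepared".

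**The concern.** The count and the percentage in Section 9.2 cannot both be right if the trial has 10 patients. The count is what starts the analysis, so this is more than a mislabelled fraction. Taken literally, the interim waits until all planned patients have been treated and followed for a week. An interim safety review mainly serves to inform whether and how the remaining patients are exposed, and at that point none remain.

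Safety is the primary objective, and Section 3.1 says no formal phase 1 trial has yet been done. The protocol promises a formal safety evaluation part-way through that its own numbers make impossible at that time. A late interim would still have some use: it could affect follow-up to weeks 6 and 12 for recent patients, or what patients are told. It could not affect dosing.

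**Working it through.** **Inputs.** Planned total: N = 10 at most (Sections 2 and 5.3). Replacement: none (Section 5.3). Interim count: 10 patients past Visit 3, stated as 50% (Section 9.2). Visit 3: one week after the single treatment session (Sections 7.2 and 9.2).

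**Step 1: reproduce the stated fraction.**
- Interim count / planned total = 10/10 = 100%. The stated 50% is not reproduced.
- Total implied by the stated fraction = 10/0.50 = 20. No section states this total.
- Half of the stated total = 0.50 × 10 = 5.

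**Step 2: patients still undosed at the interim.**
- As written: 10 − 10 = 0.
- With a trigger at 5: at most 10 − 5 = 5. This is a maximum, because no enrolment pause is stated and more patients may be dosed before the fifth reaches Visit 3.

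**Step 3: chance that the trigger is never met.** If fewer than 10 patients enrol, the trigger cannot be met. If all 10 are dosed, let *d* be the probability that a patient misses Visit 3, independently between patients. The documents give no value, so *d* is an assumption and a range is shown. The 10-of-10 trigger fails with probability 1 − (1 − *d*)^10. A 5-of-10 trigger fails with probability P(X ≤ 4), where X is binomial with 10 trials and success probability 1 − *d*.

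| Assumed *d* | 10-of-10 trigger never met | 5-of-10 trigger never met |
|---|---|---|
| 2% | 1 − 0.98^10 = 18.3% | below 0.001% |
| 5% | 1 − 0.95^10 = 40.1% | below 0.001% |
| 10% | 1 − 0.90^10 = 65.1% | 0.015% |
| 20% | 1 − 0.80^10 = 89.3% | 0.64% |

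The last column requires five completed Visits 3. Also counting patients who discontinue after dosing would lower these figures further.

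**Step 4: what a look at 5 patients could show.** With an assumed true SAE rate *p* per patient, the chance of at least one SAE in 5 is 1 − (1 − *p*)^5: 22.6% at *p* = 5%, 41.0% at 10% and 67.2% at 20%.

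**Step 5: does Section 8.1 settle the count?** The bracketed 10 can be read in two ways. If it describes the whole anticipated enrolment, the report is due at 5 enrolled, which agrees with Sections 2 and 5.3. If it describes the half, the anticipated total is 20, which agrees with the percentage in Section 9.2. The text does not decide between them. On either reading the count is of enrolled patients, who may not yet be dosed, since treatment follows screening by about four weeks (Section 7.2). The eight-month limb depends on no count.

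**The case against.** The strongest reply is that other safeguards exist and the slip is a leftover numeral.

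- **The IRB report.** Section 8.1 guarantees a safety report by eight months even if the interim never triggers, and with N = 10 the natural reading of its count limb is 5 enrolled. This stands as a real partial safeguard. However, the report is not called the interim analysis, its content and effect on dosing are not specified, and its count limb is ambiguous. The calendar limb may also come late. Section 5.4 gives a 1-year trial with about 4 months per patient. If the year includes follow-up, enrolment ends near month 12 − 4 = 8 and the last dose falls about four weeks later, so little dosing may remain.
- **Continuous reporting.** Section 8.1 provides for "training all co-investigators to report research-related adverse events to Investigator within 12 hours", with qualifying events going to the IRB and FDA. Full reports must reassess risk and benefit, possible changes to the protocol or consent form, and "whether any additional information needs to be given to the subjects who are already enrolled". That is a trial-level judgement, but it is prompted by individual qualifying events. It only partly replaces a planned cumulative review.
- **Limited gain from the correction.** Section 9.2 states no pause or decision rule, so the 5 undosed patients are an upper limit, and a look at 5 would show no SAE 77% of the time at an assumed 5% rate (100% − 22.6%). Both points are correct. They limit the benefit of a mid-trial look but do not support a trigger that rules one out.
- **No inferential consequence.** No type I error, power or final safety estimate depends on the interim. That is true; the defect concerns monitoring during the trial, not the final analysis.
- **Assumed rates.** The failure probabilities rest on miss rates that the documents do not supply. This is also true, but the contradiction and the count of 0 undosed patients need no assumption.

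**Conclusion.** The concern holds, and Section 9.2 is wrong as written. With the stated total of 10, the interim comes at 100% of patients instead of 50%, with 0 planned patients left to dose, and it is lost altogether if a single Visit 3 is missed or fewer than 10 enrol. That conclusion rests only on the protocol's own numbers. The chance of losing the interim, 18% to 89%, depends on assumed miss rates of 2% to 20%, on all 10 patients being dosed and on independence between patients. The Section 8.1 report and event reporting soften the consequence without removing it. Because this is the trial's one planned formal safety evaluation before completion, and safety is the primary objective, it must be corrected.

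**What to change.** Reconcile Sections 2, 5.3, 8.1 and 9.2 on the planned total and on the interim count. The sponsor must say which total is intended.

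- **If 10 stands:** in Section 9.2, set the trigger at *5 dosed patients (50% of the planned 10) who have completed Visit 3 or discontinued after dosing before it*. Counting dosed patients keeps those who withdraw before treatment out of the count; counting post-dose discontinuations prevents early losses from blocking the review. In Section 8.1, write the count limb as half of anticipated enrolment, 5 of 10 subjects. The eight-month limb is unaffected.
- **If 20 was intended:** leave the interim count at 10, correct Sections 2 and 5.3 to 20, and word Section 8.1 as 10 of 20.

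The first option is a short wording amendment needing IRB approval under Section 10, with no extra patients or procedures. The second also needs IRB approval and means 10 more patients than Sections 2 and 5.3 now state. Neither option settles whether dosing continues while the interim is prepared, on which the protocol is silent.
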